Treatment site assessment		X		X	X	X		X	X	Conduct after cryo-lipolysis treatments and prior to massage at Visits 2 and 6.
Height	X									
Weight	X	X		X	X			X	X	Conduct before cryo-lipolysis treatments at Visits 2 and 6.
2D/3D Photography 	X	X		X	X			X	X	See Section 8.1.2, conduct before cryo-lipolysis treatment at Visits 2 and 6
Cryolipolysis Treatment		X				X				See Section 6
Pain Assessment		X	X	X	X	X	X	X	X	See Section 8.2.1

- 1a Phone follow-up should be scheduled 7 days from last treatment visit day in instance where participant received treatment session #1 over multiple days.
- 1b If, during this phone follow-up, any of the following local effects of erythema, bruising, swelling, and/or sensory alteration are reported related to treatment session #1, additional phone follow-up (or in-person visit if aligned to planned study visit) will be scheduled in accordance with the time criteria outlined in Table 2-1 for potential AE categorization.
- 2a Phone follow-up should be scheduled 7 days from last treatment visit day in instance where participant received treatment session #2 over multiple days.
- 2b If, during this phone follow-up, any of the following local effects of erythema, bruising, swelling, and/or sensory alteration are reported related to treatment session #2, additional phone follow-up (or in-person visit if aligned to planned study visit) will be scheduled in accordance with the time criteria outlined in Table 2-1 for potential AE categorization.
-  If a participant receives only one treatment session for specific body area(s), the participant will return at Visit 8 for the 12-week post-treatment session #1 follow up assessment and study exit. If a participant receives two treatment sessions to any or all treated body areas, participant will return at Visit 9 for 12-week post-treatment session #2 follow-up and study exit. If a participant receives only one treatment session to one specific body area and two treatment sessions to another specific body area, the participant will return for Visit 8 for 12-week follow-up for the body area that received only one treatment session and Visit 9 for 12-week follow-up of body area that received two treatment sessions. The exit for this participant is Visit 9.
-  For select study sites with 3D camera system, 3D images will also be taken at this time.

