### 3. Objectives and Measures

Objectives	Measures

To evaluate participant satisfaction and effectiveness of the CoolSculpting Elite System using CoolSculpting Elite applicators for non-invasive subcutaneous fat reduction of the abdomen and flanks, upper arms, inner thighs, outer thighs and submental area
	
 
• Cryolipolysis Satisfaction Questionnaire (CSQ)-Midsection (abdomen and flanks)
 
• CSQ-Overall (if additional body area(s) beyond abdomen and flanks are treated)
 
• CSQ for individual additional body areas treated (upper arms, inner thighs, outer thighs, submental area)
 
• Cryolipolysis General Procedure Questionnaire (CGPQ)
 
• Cryolipolysis Psychosocial Impact Questionnaire (CPIQ)
 
• Participant Evaluation of Noticeable Improvement
 
• Photography and independent photography review (IPR)
 
• 3D imaging of change in volume of fat
 

To evaluate safety of the CoolSculpting Elite System using CoolSculpting Elite applicators for non-invasive subcutaneous fat reduction of the abdomen and flanks, upper arms, inner thighs, outer thighs and submental area
	
 
• Adverse events (AEs) and adverse device effects (ADEs); serious adverse events (SAEs), serious adverse device effects (SADEs)
 
• Unanticipated AEs or SAEs (previously unknown to the device)
 
• Pain assessment
 

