### 5.1. Inclusion Criteria

Participants are eligible to be included in the study only if all of the following criteria apply:

1. Participant must be in good health as determined by medical history, physical examination, vital signs, and investigator's judgment, including no known active pandemic infection.
2. Participant (healthy volunteers) has read and signed the study written ICF.
3. Male or female participant 22 to 65 years of age inclusive at screening.
4. Participant has clearly visible and palpable fat in the abdomen and flanks, and participant may also be assessed for visible and palpable fat in one or more of the following body areas: left and right lower aspects of the upper arms, left and right inner thigh, left and right outer thigh, or submental area, which in the investigator's opinion is appropriate for and may benefit from treatment.
5. Participant agrees to receive treatment of the abdomen and flanks (collectively, the midsection) and has option to receive treatment to at least 1 additional body area listed in criterion 4.
6. Participant has not had weight change fluctuations exceeding 5% of body weight in the preceding month.
7. Participant has a BMI of  $\geq 18.5$  and  $< 30$ . BMI is defined as weight in kilograms divided by height in meters squared ( $\text{kg}/\text{m}^2$ ).
8. Participant agrees to maintain weight (ie, within 5% of body weight) by not making any changes in diet or exercise routine during the course of the study.
9. Participant agrees to have photographs taken of the treatment area(s) during the scheduled time periods.

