### 8.1. Effectiveness Assessments

Effectiveness assessments will include the CSQ (6 versions), CGPQ, CPIQ, Participant Evaluation of Noticeable Improvement, independent photo review of 2D participant before and after photos, and 3D imaging to assess volumetric change of treated area, where available. ■■■■■

Planned time points for all effectiveness assessments are provided in the SoA (Table 1-1).

If travel restrictions or other changes in local regulations in the case of a pandemic or natural disaster prevent the participant from in-person visits, some study assessments may be conducted remotely or via phone or video conference.

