### **8.1.2. Photography**

A series of baseline and follow-up 2D photographs of the treatment areas will be taken using standardized set-up, lighting, and camera settings to ensure consistency. Where participant identifiable markings are seen within the treatment area, the images containing these markings will be masked for the purpose of publications but kept as part of the study record in the trial master file. The photographs may be cropped or re-sized for comparison purposes but otherwise will not be re-touched or altered in any way. Image files will be stored electronically by the sponsor in addition to Canfield Scientific (Parsippany, New Jersey, USA) and indexed by participant identifier. Participant photographs will be filed at the clinical site.

Photos will be reviewed by a blinded independent panel of three physician reviewers with expertise in the areas of dermatology and/or plastic surgery. All photographs will be blinded by removing the participant identification and dates of the photographs. The reviewers will be presented with two series of photographs for each treatment area, the pre-treatment and the post-treatment series, and asked to select the series representing the pre-treatment photographs. Post-treatment images will correspond to 4-weeks post treatment session 1 and 12-weeks post final treatment session for the respective treated body areas. The order in which the photographs are presented will be randomized by participant. The order in which the pre- and post-treatment series are presented will also be randomized. The reviewers will be asked to select the baseline photograph series for each treatment area and record their data on individual data collection forms provided by the sponsor.

Select study sites that have access to Canfield 3D imaging system will also capture 3D images for purposes of assessment of volumetric changes. The 3D imaging system will be used to obtain a 360 degree image of the body to allow quantification of the treated areas, specifically, volumetric changes from baseline.

For additional detail regarding participant photography, please see documentation created by Canfield Scientific (imaging vendor).

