#### 9.4.4. Exploratory Effectiveness Endpoints

The analyses on the exploratory endpoints will include:

- Psychosocial impact for non-invasive fat reduction in CoolSculpting participants using the CPIQ
- Experience with fat reduction procedure using the CGPQ
- Improvement in fit of clothing using CSQ-Midsection Item #2
- Proportion of participants reporting noticeable improvement at 4-weeks post treatment session 1
- 3D volumetric change from baseline

- Correct identification of baseline vs 4-week post treatment session 1 images of the treated body area(s) by at least two out of three blinded, independent reviewers for the following body areas:
  - Midsection
  - Upper arms
  - Inner thighs
  - Outer thighs
  - Submental area

Success will be defined as at least 70% correct identification of the pre-treatment images.

Exploratory effectiveness endpoints will be summarized similar to the primary effectiveness endpoint with 95% CIs.

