#### 9.5.2

#### Main Analysis of Exploratory Efficacy Endpoints

- [REDACTED]
- [REDACTED]

[REDACTED]

In addition, two-sided 95% CI on mean change from baseline by visit will be calculated based on the paired t-test. P-value on change from baseline by visit will be provided based on the paired t-test.

The number and percentage of participants in each category for each item of CGPQ at Week 12 (Visit 8) for participants who receive 1 treatment session, or at Week 20 (Visit 9) for participants who receive 2 treatment sessions, or at 12 weeks +14 days post treatment session 2 for participants who had their treatment session 2 rescheduled because of the CoolSculpting® Elite treatment hold in the US on / after 24th August 2021 will be summarized for the Evaluable Population 1 and Evaluable Population 4.

The number and percentage of participants in each category of CSQ-Midsection Item 2 at Week 12 (Visit 8) for participants who receive 1 treatment session, or at Week 20 (Visit 9) for participants who receive 2 treatment sessions, or at 12 weeks +14 days post treatment session 2 for participants who had their treatment session 2 rescheduled because of the CoolSculpting® Elite treatment hold in the US on / after 24th August 2021 will be summarized for the Evaluable Population 1 and the two-sided Fisher's exact 95% CI on the percentage of participants with improvement (a lot of improvement, moderate improvement, and a little improvement) will be provided.

The number and percentage of participants reporting noticeable improvement in any treated body area, all treated body areas, and each treated body area at Week 4 (Visit 4) post treatment session 1 will be summarized for the Evaluable Population 1 (midsection) and Evaluable Population 2 (other treated body areas) and Evaluable Population 3 (any treated body area, all treated body areas) and the two-sided Fisher's exact 95% CI on the percentage will be provided.

For midsection, the descriptive statistics of the adjusted total volume of fat (cc) at baseline and post-baseline visits, [REDACTED]

[REDACTED]

For outer thigh (left, right, and combined left and right) and submental area, the descriptive statistics of the volume of fat (cc) change from baseline values will be provided for the Evaluable Population 2.

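### The exploratory 3D result is labelled volume of fat, but the only method described is a body image giving treated-area volume, and no visible text says how fat is separated from other tissue

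*SAP*

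**What the plan says.** For the midsection, SAP 9.5.2 plans "For midsection, the descriptive statistics of the adjusted total volume of fat (cc) at baseline and post-baseline visits"; the rest of that sentence is redacted. For the outer thigh "and submental area, the descriptive statistics of the volume of fat (cc) change from baseline values will be provided for the Evaluable Population 2". The measures table in Protocol Section 3 lists "3D imaging of change in volume of fat", and the synopsis table carries the same entry.

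On the instrument, footnote 4 to the schedule of activities says "For select study sites with 3D camera system, 3D images will also be taken at this time". Protocol 8.1.2 adds "The 3D imaging system will be used to obtain a 360 degree image of the body to allow quantification of the treated areas", specifies volumetric change from baseline as the quantity, and refers to the imaging vendor's documentation for further photography detail.

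Elsewhere the protocol does not name fat as the measured quantity. Section 8.1 has "3D imaging to assess volumetric change of treated area, where available", and the endpoint list in Section 9.4.4 has "3D volumetric change from baseline". Sections 2.2 and 4.2 also speak only of volumetric measurements or changes.

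On weight, inclusion criterion 8 begins "Participant agrees to maintain weight (ie, within 5% of body weight" and rules out changes in diet or exercise.

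**The concern.** A camera image of the body gives the shape of a region and hence a volume. To call that volume fat needs a further step, either a tissue-specific measurement or a stated derivation, and none is visible. A table titled volume of fat would tell readers that the cc are fat, which the described method does not show.

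The label carries weight because the study has one arm. No control group shows how much regional volume would have changed without treatment, and body weight may move within the 5% tolerance. The midsection has a further difficulty: the SAP tabulates a baseline value as well as post-baseline values, under a title of total fat volume. At baseline there is no treatment change to interpret, so the figure is simply whatever the imaged region contains.

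**Working it through.** **Label against method**

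| Place | Output described as |
|---|---|
| SAP 9.5.2, midsection | adjusted total fat volume, cc, at baseline and later visits |
| SAP 9.5.2, outer thigh and submental area | change in fat volume, cc |
| Protocol 1.1 and 3, measures tables | change in fat volume |
| Protocol 2.2 and 4.2 | volumetric measurement or change |
| Protocol 8.1, 8.1.2 and 9.4.4 | volumetric change |

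The described instrument supports the last two rows. The first three go further, and no visible text bridges the gap: ultrasound, calipers, cross-sectional imaging and any derivation of fat from the image are all absent. That a camera records shape and not tissue composition is my inference from the description; the documents do not say it in those terms.

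**Is weight handled?** In Table 1-1, weight and 2D/3D photography are both taken at Visits 1, 2, 4, 5, 8 and 9, so same-visit weight exists for every scheduled image. The visible SAP summarises weight only as a baseline characteristic (7.1). For the midsection, the word *adjusted* is printed but not defined in visible text, and what follows is redacted, so a weight correction may exist. The visible sentence on the outer thigh and submental area contains no such word.

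**Illustration of scale.** The plan gives no figure for the 3D endpoint, so there is none to reproduce. Its sample size (96 completers, about 110 recruited) concerns the primary endpoint and is unaffected.

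Formula: volume change (cc) = weight change (kg) ÷ tissue density (kg/L) × share of the change in the region × 1000.

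- From the documents: the 5% tolerance and BMI from 18.5 to below 30.
- Assumed: body weight or height, density, and regional share.

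For one participant of 70 kg at the limit:
- 0.05 × 70 = 3.5 kg
- 3.5 ÷ 0.9 = 3.89 L for the whole body
- midsection share 10%, 20% or 30%: about 389, 778 or 1167 cc

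For a wider range, take heights of 1.55 to 1.80 m. The BMI limits then give about 44.4 to 96.9 kg, and 5% is about 2.2 to 4.8 kg:
- low end: 2.2 ÷ 1.05 × 10% = about 210 cc
- high end: 4.8 ÷ 0.9 × 30% = 1600 cc

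Per 1 kg of weight change:
- low end: 1 ÷ 1.05 × 10% = about 95 cc
- high end: 1 ÷ 0.9 × 30% = about 333 cc

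These shares are for the midsection. The formula is linear, so in any region each percentage point of share is worth 3.89 L × 1% = about 39 cc in the 3.5 kg case. The documents give no share for the outer thigh or submental area, and I assume none.

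For a group, the expected shift in mean volume is the per-kg figure times the mean weight change. If mean weight change is near zero, so is the shift, however wide the individual range.

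**The case against.** The strongest reply is that much of the relevant text cannot be seen. The midsection sentence breaks off at a redaction, the SAP's exploratory endpoint lists are blacked out, and the vendor's documentation is not available. A definition of *adjusted*, or a weight correction, may stand there. This is right. A reader might infer that midsection volume is analysed with no regard to weight; the documents do not support that. They also cannot settle what the vendor's software computes. What remains is that no visible text derives fat from the image, and that a correction for weight alone would not identify the tissue.

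Three other stronger readings also fail:

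- **Swelling creates an apparent fat loss.** Swelling of up to one month is an anticipated effect (Protocol Table 2-1), and Visit 4 falls at Day 28 + 10 days. But residual swelling adds volume relative to an untreated baseline, so it would hide a reduction and not produce one.
- **The result is biased by several hundred cc.** The illustration is one person at the outer limit, in either direction. Moving a group mean that far would need everyone to shift 5% the same way, although all agreed to keep their weight stable. The documents give no expected device effect in cc for comparison.
- **The protocol also reports a total fat volume in cc.** Its measures tables give neither cc nor a baseline total. Only the SAP does, and only for the midsection; for the outer thigh and submental area it plans change from baseline.

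It is also fair that a regression on weight change conditions on something measured after treatment, in what may be a small subset. That argues for a supportive summary, not a replacement analysis.

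**Conclusion.** The point holds as one of labelling and attribution. The label goes beyond the method described and beyond the protocol's own endpoint wording, so the cc cannot be read as fat alone. For weight, the gap is visible for the outer thigh and submental area and undetermined for the midsection.

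The cc figures show only that the tolerated weight change is not trivial for an individual; they rest on assumed weight or height, density and regional share. The conclusion about the label rests on none of these, only on reading the camera description as a measure of shape.

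The importance is low. The endpoint is exploratory, collected at select sites, and its visible analysis is descriptive. Neither the primary analysis nor the sample size is touched.

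**What to change.** In SAP 9.5.2 and the related table titles:

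1. Use the protocol's volumetric term: change from baseline in treated-area volume (cc) by 3D imaging.
2. Do not present the midsection baseline value as a total fat volume.
3. State that the method does not distinguish fat from other tissue.
4. For the outer thigh and submental area, and for the midsection if the redacted adjustment does not already cover weight, show same-visit weight change beside volume change. Add one supportive summary, for example the intercept *a*, with its 95% CI, from volume change = *a* + *b* × weight change, which estimates volume change at zero weight change.

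The cost is a SAP revision, a few table titles and a small extra analysis in a subset of sites, with no new data. The label becomes less favourable, and the intercept may be imprecise if few participants were imaged. The two protocol measures tables could be aligned at a later amendment, which would need IRB/IEC approval; the SAP change need not wait for it.

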### 4.0 Analysis Populations

The following population sets will be used for the statistical analyses.

The Enrolled Population will consist of all participants who signed the informed consent.

The Safety Population will consist of all enrolled participants who received at least one cryolipolysis treatment cycle (started or completed).

The Evaluable Population 1 will consist of all participants who completed the cryolipolysis treatment plan to the midsection and completed the CSQ-Midsection Item 1 at 12 weeks after the final treatment measured at Visit 8 (Week 12) for participants who receive 1 treatment session, or at Visit 9 (Week 20) for participants who receive 2 treatment sessions, or at 12 weeks +14 days post treatment session 2 for participants who had their treatment session 2 rescheduled because of the CoolSculpting® Elite treatment hold in the US on / after 24th August 2021, and do not have any significant protocol deviation or violation.

The Evaluable Population 2 will consist of all participants who completed the cryolipolysis treatment plan for any other body areas (Upper Arms, Inner Thighs, Outer

Thighs and Submental Area) whether midsection treatment is completed or not, and do not have any significant protocol deviation or violation .

The Evaluable Population 3 will consist of all participants who completed the cryolipolysis treatment plan for any body areas (Midsection, Upper Arms, Inner Thighs, Outer Thighs and Submental Area) and do not have any significant protocol deviation or violation.

The Evaluable Population 4 will consist of all participants who completed the cryolipolysis treatment plan to the midsection and one or more additional body areas (Upper Arms, Inner Thighs, Outer Thighs and Submental Area) and do not have any significant protocol deviation or violation.

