The number and percentage of participants with correct identification of baseline vs. 4-week post treatment session 1 by 2/3 and 3/3 blinded, independent reviewers for the following body areas will be summarized for the Evaluable Population 1 (midsection) and Evaluable Population 2 (other treated body areas) and the two-sided Fisher's exact 95% CI on the percentage will be provided:

- Midsection
- Upper arms
- Inner thighs
- Outer thighs
- Submental area

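### Midsection Week 4 results are dropped for participants who later miss the 12-week questionnaire, do not complete a planned second session or have a significant deviation

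*SAP*

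**What the plan says.** SAP 9.5.2 plans two analyses at Week 4. One counts participants "reporting noticeable improvement in any treated body area, all treated body areas, and each treated body area at Week 4 (Visit 4"). The other counts participants with "correct identification of baseline vs. 4-week post treatment session 1 by 2/3 and 3/3 blinded, independent reviewers". Both "will be summarized for the Evaluable Population 1 (midsection) and Evaluable Population 2 (other treated body areas"). The any-area and all-areas summaries of noticeable improvement use Evaluable Population 3.

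SAP 4.0 defines these sets:

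- Population 1: participants who "completed the cryolipolysis treatment plan to the midsection and completed the CSQ-Midsection Item 1 at 12 weeks after the final treatment".
- Population 2: "The Evaluable Population 2 will consist of all participants who completed the cryolipolysis treatment plan for any other body areas". There is no questionnaire condition.
- Population 3: "The Evaluable Population 3 will consist of all participants who completed the cryolipolysis treatment plan for any body areas". Again there is no questionnaire condition.
- All of them require that participants "do not have any significant protocol deviation or violation". SAP 7.5 counts timeframe deviations among the significant categories.

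SAP 9.2 rules out imputation. Protocol 9.3 ties the questionnaire condition to the evaluable population for the primary endpoint only. Protocol 9.4.4 lists both Week 4 endpoints as exploratory and sets a success line of at least 70% correct for the Week 4 photo review.

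**The concern.** A Week 4 endpoint describes what is seen about a month after session 1. Whether a participant counts in it should depend on what is known by then. For the midsection, membership instead depends on a form completed at Week 12, Week 20 or later. It also depends on finishing a second session where one was planned, and on staying free of significant deviations to the end. Someone with a usable Visit 4 answer and usable Visit 4 photographs who then leaves is removed from both results. The photo review does not use the satisfaction questionnaire at all, yet a blank form removes the photographs.

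The sets also disagree with each other. Population 3 has no questionnaire condition, so one participant's Visit 4 midsection answer can count in the any-area row and be missing from the midsection row.

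At stake are the accuracy of two early descriptive rates, one of them held against a 70% line, and the needless loss of data already collected.

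**Working it through.** **Timing (Protocol 4.1; SAP 1.0 for the treatment hold).**

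- Visit 4: Day 28 + 10.
- Session 2 (optional): Day 56 + 14, or later for participants affected by the US treatment hold.
- Questionnaire for Population 1: Day 84 + 14 after one session, Day 140 + 14 after two, or later after the hold.
- Nominal gap from Visit 4 to the questionnaire: 84 − 28 = 56 days (8 weeks), or 140 − 28 = 112 days (16 weeks).

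**Which conditions lie after Week 4.**

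- Questionnaire answered: always later, but required for the midsection only.
- Plan completed: later only for an area planned for two sessions. A one-session plan ends within 7 days of the first treatment at Visit 2.
- No significant deviation: partly later. A failed eligibility criterion precedes Week 4; a late follow-up visit does not.

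**The plan's own figures (SAP 2.4).** The exact (Clopper-Pearson) interval at n = 96 and a rate of 0.639 is 0.5346 to 0.7346, width 0.19996, which matches the stated 0.2. Recruitment is 96 / 0.88 = 109.1, about 110 as stated. Neither figure is in dispute. They give the scale: 110 − 96 = 14 planned participants without the primary assessment, and 14 / 110 = 12.7%.

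**Shift in a Week 4 rate.** With f the excluded share among those with Week 4 data:

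rate in included − rate in all = f × (rate in included − rate in excluded)

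The documents do not give the gap between included and excluded, so a range is shown. With f = 0.127 (assuming that all 14 had Week 4 data):

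| Gap (points) | Shift (points) |
|---|---|
| 10 | 1.3 |
| 20 | 2.5 |
| 30 | 3.8 |
| 50 | 6.4 |

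A negative gap gives the same shift in the other direction.

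**Against the 70% line.** The smallest pass in 96 is 68/96 = 70.8% (67/96 = 69.8% fails). Adding the 14:

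- none correctly identified: 68/110 = 61.8%
- 7 correct: 75/110 = 68.2%
- 8 correct: 76/110 = 69.1%
- 9 correct: 77/110 = 70.0%
- all 14 correct: 82/110 = 74.5%

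A minimal pass therefore survives only if at least 9 of the 14 are correct.

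**If half of the 14 left before Visit 4 (assumption).** Then 7 have Week 4 data and the total is 103. The range narrows to 68/103 = 66.0% through 75/103 = 72.8%. A 30-point gap then shifts the rate by 7/103 × 30 = 2.0 points.

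**The case against.** The strongest reply concerns scope and weight. A reader might infer that every Week 4 result is limited to people who finished all treatment and returned the 12-week form. The documents do not say that. Populations 2 and 3 have no questionnaire condition, and a completed plan for one qualifying area is enough to enter them. For an area planned for one session, completion falls before Visit 4. The deviation rule also removes people for reasons that precede Week 4. The term treatment plan is not closely defined and session 2 is optional, so it is unclear how many people plan completion would exclude. All of this stands, and it limits the main point to the midsection.

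A reader might also infer that the Week 4 rates are inflated. Nothing in the documents shows that those excluded did worse. A participant unimpressed at Week 4 may stay for a second session, and blinded physicians judge the photographs. This stands too.

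The planned attrition is 12% or less and includes people lost before Visit 4, whom no change of population recovers. Shifts of 1 to 4 points are small beside an interval about 20 points wide. One set per area also keeps the Week 4 and Week 12 denominators equal. These points lower the importance but do not justify the questionnaire condition, which Protocol 9.3 attaches only to the primary endpoint.

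Finally, SAP 3.3, 9.5.1 and parts of 9.5.2 and 9.6 are blacked out, so a further Week 4 analysis cannot be excluded. None is visible.

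**Conclusion.** The point holds for the midsection: both Week 4 endpoints are conditioned on a later questionnaire, on a second session where one was planned, and on later deviations. For other areas and for the any-area and all-areas summaries, it holds only through two-session plans and later deviations.

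The size cannot be fixed from the documents. At planned attrition the shift is 1.3 to 6.4 points for gaps of 10 to 50 points, provided all 14 non-completers had Week 4 data. That proviso is an upper limit for attrition. Losses before Visit 4 reduce the effect; deviation exclusions come on top of attrition, and no figure is given for them. A photo result just above 70% could change sides; one well above it would not.

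Severity is low. The endpoints are exploratory, the study has one arm and no hypothesis is tested.

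**What to change.** In SAP 9.5.2, analyse both Week 4 endpoints in all participants who received session 1 to the area and have a Week 4 assessment of it. Keep the evaluable-population versions as supplementary tables and show n in each. Record the departure from Protocol 9.4.1, which bases effectiveness analyses on the evaluable population, so that the two documents agree.

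At minimum, remove the 12-week questionnaire condition from the midsection Week 4 analyses. The 12-week photo analysis is a separate matter and need not change for this point.

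The cost is SAP wording, a matching note against the protocol and one population flag; no new data are needed. The downside is that denominators will differ between the Week 4 and Week 12 tables.
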